7.3.2 Method of Detecting Adverse Events and Serious Adverse Events

Care will be taken not to introduce bias when detecting AEs and/or SAEs. Open-ended and non-leading verbal questioning of the subject is the preferred method to inquire about AE occurrences.

7.3.3 Follow-up of Adverse Events and Serious Adverse Events

After the initial AE/SAE report, the investigator is required to proactively follow each subject at subsequent visits/contacts. All SAEs and AEs of special interest (AESI) (as defined in [Section 7.3.6 Adverse Events of Special Interest]) will be followed until resolution, stabilization, the event is otherwise explained, or the subject is lost to follow-up (as defined in [Section 8.3 Lost to Follow-up]). Further information on follow-up procedures is provided in [Section 10.3 Appendix 3 Adverse Events: Definitions and Procedures for Recording, Evaluating, Follow-up and Reporting].

If after the protocol-defined AE collection period (see [Section 7.3.1 Time Period for Collecting Adverse Event and Serious Adverse Event Information]), an AE progresses to an SAE, or the investigator learns of any (S)AE (serious adverse event or adverse event) including death, where he/she considers there is reasonable possibility it is related to the IP or study participation, the investigator must promptly notify the sponsor.

7.3.4 Regulatory Reporting Requirements for Serious Adverse Events

- Prompt notification by the investigator to the sponsor of a SAE within 24 hours is essential so that legal obligations and ethical responsibilities towards the safety of subjects and the safety of a study IP under clinical investigation are met.
- The sponsor has a legal responsibility to notify both the local regulatory authority and other regulatory agencies about the safety of a study IP under clinical investigation. The sponsor will comply with country-specific regulatory requirements relating to safety reporting to the regulatory authority, IRB/IEC and investigators.
- Investigator safety reports must be prepared for suspected unexpected serious adverse reactions (SUSAR) according to local regulatory requirements and sponsor policy and forwarded to investigators as necessary.
- An investigator who receives an investigator safety report describing a SAE or other specific safety information (e.g., summary or listing of SAEs) from the sponsor will review and then file it along with the Investigator's Brochure and will notify the IRB/IEC, if appropriate according to local requirements.

7.3.5 Disease-related Events and/or Disease-related Outcomes Not Qualifying as Adverse Events or Serious Adverse Events

Under this protocol, the following event(s) will not be considered as an (S)AE:

Disease progression: events including defined study endpoints that are clearly consistent with the expected pattern of progression of the underlying disease are not to be recorded as (S)AEs. These data will be captured as efficacy assessment data as outlined in [Section 7.1 Efficacy Assessments]. If there is any uncertainty as to whether an event is due to anticipated disease progression and/or if there is evidence suggesting a causal relationship between the IP and the event, it should be reported as an (S)AE. All deaths up to 30 days after the final administration of IP must be reported as an SAE, even if attributed to disease progression.

7.3.6 Adverse Events of Special Interest

AEs (serious or nonserious) of special interest are to be collected via the SAE worksheet and reported within 24 hours as described in [Section 10.3.6 Reporting Procedures for Serious Adverse Events].

AESI are AEs the sponsor may wish to carefully monitor. These AEs may be serious or non-serious and should be reported on the eCRF and the SAE worksheet. These AEs are not considered SAEs unless they meet the definition of an SAE. AESI in this study will include:

- Increased heart rate and tachycardia
- Increased blood pressure
- Hypersensitivity reactions
- Urinary retention
- QT prolongation

7.3.7 Special Situations

Certain special situations observed in association with the IP, such as incorrect administration (e.g., wrong dose of IP or background therapy) are reported as protocol deviations and/or may require special reporting, as described below. These special situations are not considered AEs, but do require to be communicated to Astellas as per the timelines defined below.

If a special situation is associated with, or results in, an AE, the AE is to be assessed separately from the special situation and captured as an AE in the eCRF. If the AE meets the definition of an SAE, the SAE is to be reported as described in [Section 10.3.6 Reporting Procedures for Serious Adverse Events] and the details of the associated special situation are to be included in the clinical description on the special situation worksheet or pregnancy reporting form.

The special situations are:

- Pregnancy
- Lactation
- Medication error, overdose and off-label use
- Misuse/abuse
- Occupational exposure
- Suspected drug-drug interaction

Instructions and procedures for reporting special situations are provided in [Section 10.3.7 Reporting Procedures for Special Situations].

7.4 **Pharmacokinetics**

Not applicable.

7.5 Pharmacodynamics

Not applicable.

7.6 Electronic Clinical Outcome Assessment

For this study, it has been decided that there are justifiable scientific reasons (i.e., recall bias) to limit subject reported changes to changes reported by the subject to the site within 1 business day of its entry, as changes outside of this window could potentially impact the data integrity of the study. The data under this rule should be: all subject, primary and secondary endpoints data. However, the site/investigator can remove/inactivate any data that they determine to be in error at any time with recording the reason for the removal/inactivation. The inactivated data will be accessed and reviewed by study monitors. Subject bladder diaries, questionnaires and other data completed by the subject will be entered on an electronic device (e-diary). The information on the electronic device will be automatically uploaded to a central website. The investigator or site designee should review the diaries and questionnaire data on the website for correct completion before each planned visit of the subject (on site visit for all except end of study which can be either site visit or telephone contact) and discuss the results or retrain the subject if applicable. In case clinically relevant adverse changes are noticed during review of the e-diary, these will be recorded as an AE [Section 10.3 Appendix 3 Adverse Events: Definitions and Procedures for Recording, Evaluating, Follow-up and Reporting].

The bladder e-diary, questionnaire results and other data collected in the e-diary will be transferred electronically to sponsor or designee at predefined intervals during the study. The vendor will provide sponsor or designee with a complete and clean copy of the data.

For this study the following information will be collected and entered by the subject in the e-diary (see [Section 7.2.6 Overactive Bladder Symptom Score for detailed information per visit):

- Bladder e-diary
- OABSS

The investigator must guide the subject to ensure that on the evening before and during the 2-day period of micturition volume collection, the subject's fluid intake should be regulated (as per investigator guidance) to an appropriate level considering, e.g., age, sex and subject's condition into account. The intake must remain as consistent as possible on these volume collecting days prior to visit 2/week 0 (baseline).

7.7 Other Assessments

Not applicable.

7.8 Total Amount of Blood

The total amount of blood for each subject will vary depending on the course of their disease, duration on treatment and local laboratory requirements. At any time during the study, if any laboratory abnormalities are found for a subject, additional blood may be drawn for safety monitoring.

Table 4Blood Volume

Sample Type	Number of Samples	Sample Volume (mL)	Total Volume (mL)
Clinical Laboratory Tests	2	8-10 (+5†)	25
Total			25

†Includes serology test at screening.

Additional blood may be drawn for safety reasons. The maximum amount of blood drawn during the study will not exceed 50 mL.

8 SUBJECT DISCONTINUATION

Refer to [Section 10.1.9 Study and Site Start and Closure] regarding discontinuation of study sites or of the study as a whole.

8.1 Discontinuation of Individual Subject(s) from Study Treatment

A discontinuation from treatment is defined as a subject who enrolled in the study and for whom study treatment is permanently discontinued for any reason.

The subject is free to withdraw from the study treatment and/or study for any reason and at any time without giving reason for doing so and without penalty or prejudice. The investigator is also free to discontinue the subject from study treatment or to terminate a subject's involvement in the study at any time if the subject's clinical condition warrants it.

The reason for discontinuation from study treatment must be documented in the subject's medical records.

A subject must discontinue study treatment for any of the following reasons:

- Subject requests to stop treatment
- Any clinical AEs, laboratory abnormality or intercurrent illness, in the opinion of the investigator, indicates continued treatment is not in the best interest of the subject
- If signs or symptoms of hypersensitivity to mirabegron are observed (e.g., anaphylactic reaction, erythema multiforme or exfoliative dermatitis)
- ALT or $AST > 8 \times ULN$
- ALT or $AST > 5 \times ULN$ for more than 2 weeks
- ALT or AST > 3 × ULN and TBL > 2 × ULN or international normalized ratio (INR)
 > 1.5 (if INR testing is applicable/evaluated)
- ALT or $AST > 3 \times ULN$ with the appearance of fatigue, nausea, vomiting, right upper quadrant pain or tenderness, fever, rash and/or eosinophilia (> 5%)

If a subject discontinues treatment prematurely, the subject will be encouraged to complete all scheduled visits to record all available information.

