- Submit results for any additional testing and possible etiology on the LA-CRF or an appropriate document.

Study Treatment Discontinuation

In the absence of an explanation for increased liver function tests, such as viral hepatitis, preexisting or acute liver disease, or exposure to other agents associated with liver injury, the subject may be discontinued from study treatment. The investigator may determine that it is not in the subject's best interest to continue study treatment. Discontinuation of study treatment should be considered if:

- ALT or AST $> 8 \times ULN$
- ALT or AST > $5 \times$ ULN for more than 2 weeks
- ALT or AST > 3 × ULN and† TBL > 2 × ULN or INR > 1.5) (if INR testing is applicable/evaluated)
- ALT or AST > $5 \times$ ULN and \dagger (TBL > $2 \times$ ULN in subjects with liver metastases)
- ALT or $AST > 3 \times ULN$ with the appearance of fatigue, nausea, vomiting, right upper quadrant pain or tenderness, fever, rash and/or eosinophilia (> 5%)

[†]Samples taken simultaneously or within a maximum of 24 hours.

In addition, if close monitoring for a subject with moderate or severe hepatic laboratory tests is not possible, study treatment should be discontinued.

Hy's Law definition: Drug-induced jaundice caused by hepatocellular injury, without a significant obstructive component, has a high rate of bad outcomes, from 10% to 50% mortality (or transplant).

The 2 "requirements" for Hy's Law are:

1. Evidence that a drug can cause hepatocellular-type injury, generally shown by an increase in AT elevations > 3 × ULN ("2 × ULN elevations are too common in treated and untreated subjects to be discriminating").

2. Cases of increased total bilirubin (at least 2 × ULN) with concurrent AT elevations at least 3 × ULN and no evidence of intra- or extra-hepatic bilirubin obstruction (elevated ALP) or Gilbert's syndrome [Temple, 2006].

FDA Guidance for Industry titled, "Drug-induced Liver Injury: Premarketing Clinical Evaluation" issued by the FDA on July 2009:

- 1. The drug causes hepatocellular injury, generally shown by a higher incidence of 3-fold or greater elevations above the ULN of ALT or AST than the (nonhepatotoxic) control drug or placebo.
- Among subjects showing such AT elevations, often with ATs much greater than 3 × ULN, one or more also show elevation of serum TBL to > 2 × ULN, without initial findings of cholestasis (elevated serum ALP).

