### 6.2.2 **Protocol Deviations**

The number and percentage of subjects with the following protocol deviation criteria will be summarized for each criterion and total by treatment group and total as well as by investigative site. Subjects deviating from a criterion more than once will be counted once for the corresponding criterion.

The unique identifiers will be as follows:

PD1 - Entered into the study even though they did not satisfy entry criteria

- PD2 Developed withdrawal criteria during the study and was not withdrawn
- PD3 Received wrong treatment or incorrect dose
- PD4 Received excluded concomitant treatment
- PD5 Issues related to missing or invalid baseline Diary/OABSS

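### Four liver thresholds are mandatory stopping rules in Protocol 8.1 but discretionary and conditional in Appendix 4, and no text says which prevails

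*Protocol*

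**What the plan says.** **Protocol 8.1** introduces its list with "A subject must discontinue study treatment for any of the following reasons". Beside subject request, investigator judgement and hypersensitivity, the list holds four liver criteria based on ALT or AST: above 8 × ULN; above 5 × ULN for more than 2 weeks; above 3 × ULN combined with bilirubin above 2 × ULN or INR above 1.5; and above 3 × ULN "with the appearance of fatigue, nausea, vomiting, right upper quadrant pain or tenderness, fever, rash and/or eosinophilia" (more than 5%). The list does not refer to Appendix 4.

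**Protocol 10.4, Appendix 4**, under its paragraph on study treatment discontinuation, first says that when raised liver tests have no explanation, such as viral hepatitis, existing liver disease or another hepatotoxic agent, "the subject may be discontinued from study treatment". It then writes "Discontinuation of study treatment should be considered if" and lists the same four cut-offs plus a line for subjects with liver metastases. A footnote requires the paired values to come from samples taken together or within 24 hours. The paragraph adds that treatment should stop if a subject with moderate or severe abnormalities cannot be closely monitored.

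**SAP 6.2.2** defines deviation category PD2 as "Developed withdrawal criteria during the study and was not withdrawn". It does not say which protocol section supplies the withdrawal criteria.

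**The concern.** The same laboratory result carries two instructions of different force. An investigator who reads 8.1 has no choice; one who reads Appendix 4 has a choice, and may also look first for another cause. Section 10.3.1.2 sends investigators to Appendix 4 for detailed instructions on drug-induced liver injury, so the discretionary text is the one a site handling a liver signal is pointed to.

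Two things are at stake. The first is consistent handling of subjects with marked liver abnormalities. The second is a clear definition of PD2: a subject kept on treatment after crossing a threshold has met a withdrawal criterion under 8.1, but not clearly so under Appendix 4.

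**Working it through.** No arithmetic applies and the plan gives no figure to reproduce. The check is a line-by-line comparison of the two lists in the current protocol text. I read the combined criterion as above 3 × ULN together with either bilirubin above 2 × ULN or INR above 1.5, which is the grouping used in SAP 6.5.2.1.

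| Item | Protocol 8.1 | Protocol Appendix 4 |
|---|---|---|
| Force | Mandatory | Permissive, then to be considered |
| Condition on other causes | None | Lead-in applies when no other explanation exists |
| ALT/AST > 8 × ULN | Listed | Listed, same cut-off |
| ALT/AST > 5 × ULN for more than 2 weeks | Listed | Listed, same cut-off |
| ALT/AST > 3 × ULN with TBL > 2 × ULN or INR > 1.5 | Listed, no sampling window | Listed, same cut-offs, samples simultaneous or within 24 hours |
| ALT/AST > 3 × ULN with symptoms or eosinophilia | Listed | Listed, same cut-off |
| ALT/AST > 5 × ULN with TBL > 2 × ULN, liver metastases | Not listed | Listed |
| Close monitoring not possible | Not mentioned | Treatment should be discontinued |

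1. **Overlap.** All 4 of the 4 liver criteria in 8.1 reappear in Appendix 4 with identical cut-offs.
2. **Force.** The obligation weakens from compulsory to optional.
3. **Other cause.** This is the sharpest practical difference. Take a subject with ALT above 8 × ULN and a plausible alternative cause. Under 8.1 the subject must stop. Under Appendix 4 the case for stopping is expressly tied to the lack of an explanation, and the sentence on close monitoring implies that treatment can otherwise go on. If the no-explanation condition is read as covering only the lead-in sentence and not the list, the list is still discretionary and the conflict with 8.1 remains.
4. **Sampling window.** ALT or AST above 3 × ULN and bilirubin above 2 × ULN measured more than 24 hours apart can satisfy the wording of 8.1 but not that of Appendix 4.
5. **Metastases line.** Any subject above 5 × ULN with bilirubin above 2 × ULN is also above 3 × ULN with bilirubin above 2 × ULN. On its cut-offs this line adds no new threshold; it is a difference in text only.
6. **Precedence.** Neither section says that it overrides the other.
7. **Frequency.** Protocol Table 1 schedules chemistry only at screening and at week 12/EoT, and SAP 2.2 has study drug stop at week 12/EoT. For a subject who completes treatment, no scheduled sample falls where it could prompt an early stop, so triggers would come mainly from unscheduled tests. Exclusion criterion 15 also removes subjects with ALT or AST at or above 2 × ULN or bilirubin at or above 1.5 × ULN (Gilbert's syndrome excepted for bilirubin), and INR is not in the Appendix 6 panel.

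**The case against.** The best reply is that both sections can be obeyed at once. A site that stops under 8.1 breaches nothing in Appendix 4, which never tells anyone to continue and describes its purpose as guidance for monitoring. As 8.1 is the only list in mandatory terms, it is the natural referent for PD2, and Section 7 makes any departure from the protocol a recordable deviation. This has force, but it leaves the reader to infer a precedence that the protocol does not state, while Section 10.3.1.2 points to Appendix 4. A site that follows Appendix 4 as written can still breach 8.1.

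Three stronger readings might be inferred, and the documents do not support them:

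- **That every such case is a potential drug-induced liver injury.** Section 10.3.1.2 reserves that term for ALT or AST abnormality with raised bilirubin and no other cause. Of the four criteria, only the combined one contains a bilirubin element, and it too needs other causes to be absent.
- **That subjects kept on treatment under Appendix 4 are unprotected.** That appendix calls for repeat testing within 72 hours, work-up with expert consultation, notice to the sponsor of severe abnormalities possibly attributable to study drug, and stopping if close monitoring is not possible.
- **That PD2 counts will vary by site and disturb the analysis.** Nothing says PD2 is assigned by the section a site happened to read. It is a descriptive count. The SAP defines no per-protocol set, and membership of the FAS and SAF does not depend on it.

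**Conclusion.** The inconsistency is real and sits in the current text: four shared thresholds, two levels of obligation, different conditions attached, and no rule of precedence. It bears on subject safety and merits correction. Its reach is limited. Cases should be few, given the testing schedule and the entry limits; that is a judgement from the design, since the documents give no expected rate of liver events. PD2 changes no analysis set, so no efficacy estimate changes through it. The effect on reporting is confined to a deviation category whose source text is not cited.

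The conclusion rests on reading Appendix 4's discontinuation paragraph as allowing treatment to continue when it does not say otherwise, which its sentence on close monitoring supports. It takes no position on which instruction is clinically right.

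**What to change.** Reconcile Protocol 8.1 and Appendix 4 so that each of the four shared thresholds carries one instruction, under the same conditions in both places: whether an alternative cause matters, whether the 24-hour sampling window applies, and whether the liver-metastases line belongs. A cross-reference from one section to the other would prevent the texts from drifting apart again. The sponsor's medical team decides which wording stands. In SAP 6.2.2, have PD2 cite the reconciled text as its withdrawal criteria.

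The drafting is small, but a protocol amendment needs IRB/IEC approval before implementation (Section 10.1.1). SAP Appendix 9.1 already describes 249 subjects as randomized, so at this stage the protocol change may guide few or no subjects. The PD2 citation costs one line and, under SAP Section 1, can be made at any time before database hard lock.

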8.2 Discontinuation of Individual Subject(s) from Study

All subjects who discontinue study treatment will remain in the study and must continue to be followed for protocol-specific follow-up procedures as outlined in Schedule of Assessments [Table 1]. The only exception to this is when the subject specifically withdraws

consent for any further contact with him/her or persons previously authorized by the subject to provide this information.

8.3 Lost to Follow-up

Every reasonable effort is to be made to contact any subject lost to follow-up during the course of the study to complete study-related assessments, record outstanding data and retrieve IP. These contact attempts should be documented in the subject's medical record.

9 STATISTICAL CONSIDERATIONS

9.1 Statistical Hypotheses

The hypothesis for comparisons is given as follows:

H₀: The adjusted mean change from baseline at week 12 in mean number of micturitions per 24 hours in the 50 mg group is not different from zero.

H₁: The adjusted mean change from baseline at week 12 in mean number of micturitions per 24 hours in the 50 mg group is not equal zero.

9.2 Sample Size Determination

The sample size for this study is based upon change from baseline for mean number of micturitions/24 hours within a single treatment arm. Change from baseline will be tested to determine if the change is different from zero i.e., a change in mean number of micturitions/24 hours. When the sample size is 125, a single group t-test with a 5% two-sided significance level will have 80% power to detect a change of 0.9 micturitions with a SD of 3.562 [Neurourology and Urodynamics, 2015]. Assuming 25% of the subjects will drop out, about 166 subjects will be enrolled to yield 125 evaluable subjects in 50 mg group.

9.3 **Populations for Analyses**

Population	Description
Enrolled	All subjects who sign the ICF.
Randomized	All subjects who are randomized. Subjects will be analyzed according to the study treatment to which they are randomized.
Full Analysis Set	The FAS will consist of all subjects who are randomized and receive at least 1 dose of IP and have at least 1 post baseline measurement for mean number of micturitions per 24 hours. The FAS will be analyzed by treatment arm as randomized (i.e., treatment arm based on randomization assignment). This will be the primary analysis set for efficacy analyses.
Safety Analysis Set	The SAF will consist of all subjects who took at least 1 dose of IP. The safety set will be analyzed by treatment arm as treated (i.e., based on the treatment the subject actually received rather than the treatment to which the subject was randomized).

The following populations are defined:

FAS: Full Analysis Set; ICF: informed consent form; IP: investigational product; SAF: Safety Analysis Set.

